3.0 CLINICAL INVESTIGATION DESIGN

This is a prospective, multi-center, international, single-arm, pivotal investigational study designed to evaluate the safety and effectiveness of the Aveir DR LP system in a subject population indicated for a DDD(R) pacemaker.

The clinical investigation will enroll up to 550 subjects from up to 85 participating centers from the United States, Canada, Europe, and Asia Pacific. The Sponsor may approach centers in other countries for participation in the clinical investigation as needed.

Subjects participating in the clinical investigation will be followed through at least 12 months with data collected at baseline, implant procedure, pre (hospital) discharge, and follow-up at 1 month, 3 months, 6 months, 12 months and every 6 months thereafter until study completion.

[REDACTED]
[REDACTED]
[REDACTED]

[REDACTED]
[REDACTED] Pre-market submissions to other country regulatory agencies will made be per local requirements.

The Sponsor has designed this clinical investigation to involve as little pain, discomfort, fear, and any other foreseeable risk as possible for subjects. Refer to the Risks Analysis section of this clinical investigation plan for details.

Clinical Investigation Plan for Europe

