5.4 Subject Enrollment

A patient is considered enrolled in the clinical investigation from the moment the patient provides written informed consent.

All enrolled subjects who meet eligibility criteria should undergo an attempted implant. A subject may withdraw or be withdrawn prior to the implant attempt. If an enrolled subject does not undergo an attempted implant, the subject should be withdrawn as soon as possible.

If subjects receive a device without meeting all the conditions listed above, they should still complete all follow-up requirements. These subjects are considered CIP deviations.

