5.7 Total Expected Duration of the Clinical Investigation

The expected duration of each subject's participation in the clinical study is 1 year including the scheduled visits and data collection as listed in Section 6.6. All enrolled subjects will be followed through subject withdrawal or site closure, whichever occurs first. Site closure will not begin until all active subjects across all active study sites have completed their 12-month follow up visits or the 12-month visit window has passed and approval for commercial use is received from local regulatory agencies. For more information about the clinical investigation conclusion and site closure, see Section 13.0.

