6.2.9 Subjects without any LPs implanted

Investigators will follow subjects who leave an attempted *de novo* implant procedure without any implanted Aveir LPs for a period of at least 30 days to evaluate for adverse events. At the end of the 30 days, the investigator will withdraw the subject.

The investigator must document the nature of and reasons for the unsuccessful implant on the Implant Form. Subjects who have an unsuccessful implant will not be eligible for re-implantation attempts of any Aveir LPs at a later date during the study period.

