3.2 Adverse Events

All reported adverse events (AE), serious adverse events (SAE), adverse device effects (ADE), serious adverse device effects (SADE), unanticipated adverse device effect (UADE) or unanticipated serious adverse device effect (USADE) will be summarized for all enrolled subjects using the number of events, the number of subjects with events and the percentage of subjects with events. All CEC adjudicated events will also be summarized for all enrolled subjects with the number of events, the number of subjects with events and the percentage of subjects with events. An AE listing which includes all adverse events and whether or not each event is device-related or procedure-related will be provided.

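### SAP 3.2 reports adverse events as crude percentages of all enrolled subjects with no visible per-subject time window, although follow-up is unequal by design, so the percentages refer to no defined time

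*SAP*

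**What the plan says.** SAP 3.2 (Adverse Events) covers every class of reported event and summarises it "using the number of events, the number of subjects with events and the percentage of subjects with events". It treats adjudicated events the same way: "All CEC adjudicated events will also be summarized for all enrolled subjects with the number of events". The visible text of that section names no time window, person-time or censoring rule.

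The follow-up behind those percentages varies widely.

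- **Start.** CIP 5.4: "A patient is considered enrolled in the clinical investigation from the moment the patient provides written informed consent". The denominator therefore includes people who never reach the procedure.
- **Very short.** CIP 5.4: "If an enrolled subject does not undergo an attempted implant, the subject should be withdrawn as soon as possible".
- **About a month.** CIP 6.2.9 follows de novo subjects who leave the procedure "without any implanted Aveir LPs for a period of at least 30 days to evaluate for adverse events" and then withdraws them. CIP 6.2.8 does the same after a failed upgrade, and CIP 6.4 after all LPs are removed or deactivated without replacement.
- **Open-ended.** CIP 3.0 schedules visits at "12 months and every 6 months thereafter until study completion". CIP 5.7 adds: "All enrolled subjects will be followed through subject withdrawal or site closure, whichever occurs first". Under CIP 13.0, completion requires all active subjects to be past their 12-month visit or window and local marketing approval to have been received. CIP 7.3.1 keeps event reporting open to the last visit.

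By contrast, SAP 2.3.1 and 2.3.4 estimate the two safety endpoints by Kaplan-Meier at 12 months.

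**The concern.** A percentage of subjects with an event can be interpreted only if the reader knows over what period. Here the period differs between subjects and is set partly by the calendar: when each subject was implanted, when the data are cut, and when approval arrives. The same device with the same event rates would give a higher percentage if accrual were slower or the cut later.

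CIP 1.1.2 describes this as the first in-human evaluation of the system, so these tables are the broad safety picture. They will be read next to a 12-month complication-free rate that is fixed in time and restricted to de novo subjects with an attempted implant. The two sets of figures differ in both time frame and population.

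**Working it through.** **Is there a figure to reproduce?** No. The visible documents state no expected AE percentage and no accrual period. What follows is an illustration under stated assumptions.

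**Assumptions (not in the documents).** True 12-month risk R of 5%, 10% or 20%. Follow-up at the cut is uniform over 12 to 24 months, as with 12 months of even accrual and a cut when the last subject reaches month 12. A shorter range of 12 to 18 months is also shown. There are two hazard shapes with the same R.

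Let H = −ln(1 − R).

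*Constant hazard*, follow-up uniform on [a, b] years:

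crude % = 1 − [exp(−Ha) − exp(−Hb)] / [H(b − a)]

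For R = 20%, a = 1, b = 2: H = 0.2231, exp(−H) = 0.80, exp(−2H) = 0.64. So 1 − 0.16/0.2231 = 1 − 0.717 = 28.3%.

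*Early hazard*, with 80% of the first-year hazard in month 1 and the rest even at 0.2H/11 per month, continuing after month 12. With x = 12 × 0.2H/11:

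crude % = 1 − (1 − R) × [1 − exp(−x)] / x

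For R = 20%: x = 0.0487 and [1 − exp(−x)]/x = 0.976. So 1 − 0.80 × 0.976 = 21.9%. For 12 to 18 months, replace 12 by 6 in x.

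| True 12-month risk | Constant, 12–18 mo | Constant, 12–24 mo | Early, 12–18 mo | Early, 12–24 mo |
|---|---|---|---|---|
| 5% | 6.2% | 7.4% | 5.3% | 5.5% |
| 10% | 12.3% | 14.6% | 10.5% | 11.0% |
| 20% | 24.3% | 28.3% | 21.0% | 21.9% |

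**Sensitivity to accrual and cut (R = 20%, constant hazard).** With 24 months of accrual the figure is 35.5%. If the cut comes 12 months later it is 42.6% (12 months of accrual) or 48.4% (24 months). Under the early hazard the same three cases give 23.8%, 25.6% and 27.4%.

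**Pull in the other direction.** Suppose 5% of enrolled subjects are never attempted and have no event, and 2% are followed for one month only. Under the constant hazard the one-month risk is 1 − 0.8^(1/12) = 1.8%, so 28.3% becomes 0.93 × 28.3% + 0.02 × 1.8% = 26.4%. Under the early hazard 21.9% becomes 20.7%. If everyone else had exactly 12 months, the true 20% would appear as 18.6% (constant) or 18.9% (early).

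**Target of the alternative.** A 12-month Kaplan-Meier or cumulative-incidence estimate in subjects with an attempted implant aims at R whatever the accrual or cut, provided censoring is non-informative.

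**The case against.** **The tables are descriptive.** SAP 3.2 sits under descriptive endpoints, and nothing calls its percentages 12-month risks. There is one arm, so unequal exposure cannot distort a comparison between arms. This stands. A reader might infer that the plan misstates a 12-month risk or that the safety conclusion is at stake. The documents support neither reading: both safety endpoints use Kaplan-Meier at 12 months.

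**Device complications are already covered.** Those endpoints supply the 12-month estimate for device- or procedure-related SADEs in de novo subjects. This largely stands. What they leave uncovered is all-cause SAEs, other adjudicated categories and upgrade subjects.

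**Complications come early.** CIP 4.1.1.1 cites evidence that nearly all leadless-pacemaker complications arise within 30 days, and reports that all primary-endpoint SADEs in the sponsor's previous leadless trial did so. It is tempting to apply the 28% figure to complications; on this evidence the early-hazard figure is the closer guide. That reasoning does not extend to all-cause AEs and SAEs.

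**Kaplan-Meier is available elsewhere.** SAP 2.2 and 2.2.3 and CIP 8.2.6 provide for it, but none is tied to SAP 3.2, which names only counts and percentages. SAP 3.5 is different: it lists hospitalisations and mortality without naming any statistic. A reader might infer that crude percentages are prescribed there too; the text does not say so.

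**Parts of the SAP are hidden.** SAP 2.5, 2.6, part of 2.1 and section 7.0 are blacked out, and some table content is deferred to mock-ups that are not shown. It would go too far to say that the plan contains no time limit; the point holds for the visible text. A common calendar cut in the hidden text would not answer it, because exposure would still differ between subjects. Only a per-subject limit would.

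**Conclusion.** The point holds as a minor reporting weakness. On the visible text, the SAP 3.2 percentages refer to no defined time, depend on accrual and data cut, and cannot be compared with the 12-month complication-free rate. No confirmatory test, success criterion or data collection is affected.

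The documents do not fix the size. With follow-up uniform over 12 to 24 months, a true 20% would read as about 28% under a constant hazard, the case relevant to all-cause AEs and SAEs. It would read as about 22% if 80% of the first-year hazard falls in month 1, which is closer to device- or procedure-related SADEs. Longer accrual or a later cut widens the gap. Early exits and never-attempted subjects narrow it, and can take the figure slightly below the true risk.

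**What to change.** Keep the all-enrolled counts and the AE listing, which also hold events between consent and procedure. Then:

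1. **SAP 3.2, 12-month estimate.** For subjects with an attempted implant, with time counted from the procedure, add the cumulative percentage with at least one event by day 365. Do this for all-cause SAEs and for CEC-adjudicated categories not already covered by the safety endpoints. Use Kaplan-Meier, or cumulative incidence with death as a competing event where death is not itself part of the category. Death counts as an SAE under CIP 7.1.2, so the any-SAE row needs no competing-event rule.
2. **SAP 3.2, all follow-up.** Show events over all follow-up in a separate table, with patient-years and events per 100 patient-years.
3. **SAP 3.5.** State that mortality is reported by Kaplan-Meier and hospitalisation by cumulative incidence with death competing, on the same population, time origin and day-365 limit.

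The cost is SAP wording and a few extra table columns. No new data are needed. If the hidden mock-ups already set a per-subject window, a cross-reference in SAP 3.2 would cover that part.

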3.3 Subject Early Termination

Subject early termination reasons including deaths, withdrawals, lost-to-follow-up, etc. will be summarized by treatment arms at all scheduled visits.

3.4 Protocol Deviation

Protocol deviations will be summarized by major and minor categories for subjects in whom a protocol deviation was reported.

3.5 Additional Data

The following additional data will be recorded and reported descriptively:

- Comparisons of demographics between the study population to the existing dual-chamber pacemaker population by region
- All adverse events, and whether or not each is device-related or procedure-related
- Implant success rate and reasons for unsuccessful implant

Statistical Analysis Plan

- Device handling characteristics at implant
- Number of device repositioning at time of implantation
- Implant duration, fluoroscopy duration, and time from implant to hospital discharge
- Pre-procedure (i.e. MRI, CT, X-ray) and procedural imaging (i.e. ICE) measures to evaluate the right atrium and/or the atrial LP based on any imaging data provided to the Sponsor
- Final location of LP placement
- Demographics: gender, age, ethnicity, race, indication for pacemaker implant
- Medical history
- Use of beta blocker, ACE, ARB, anti-coagulation, anti-arrhythmic, and anti-platelet medications
- Remaining device longevity at the six-month visit, as displayed by the programmer based on delivered therapy, programmed settings, percent pacing, and measured pacing impedance.
- Average base rate, impedance, pulse amplitude, pulse duration and percentage pacing will also be reported for all visits
- Hospitalizations
- Mortality
- Upgradeability of the Aveir ventricular LP (VR) into the Aveir DR LP system summarized by:
 - Success rate of VR to DR upgrades and reasons for unsuccessful upgrades.
 - Summary of adverse events related to upgrades
 - Summary of device measurements for subjects with an upgrade
- AV synchrony (at various positions and activity levels)
- EQ-5D Health-Related Quality of Life Analysis

3.6 24-Hour Holter Monitor Data Analysis

All capable *de novo* subjects will be asked to wear a 24-hour Holter monitor and complete a symptom diary, until 50 subjects provide data contributing to the analysis. The test may be performed any time after the beginning of the 3-month visit window. The preferred window to perform the 24-hour Holter test is between the 3-month and 6-month visit. These data will be examined for appropriate sensing, pacing, AV Synchrony during the activities of daily living for each subject. In addition, these data will be evaluated for any correlation between any subject symptoms with losses of AV synchrony, if present.

The Sponsor will provide a 24-hour Holter summary report to the respective in-country regulatory agency, which includes the following for each subject:

- Minimum, maximum, and average heart rate
- Percent atrial pacing
- A telemetry strip of the minimum heart rate and a telemetry strip during pacing (the pacing strip may be the same as the minimum heart rate strip but is not required).
- Number of pauses seen (defined as RR interval greater than or equal to 2 sec or < 30 bpm)
- All telemetry strips of a pause greater than the programmed lower rate limit after accounting for any hysteresis programming
- All telemetry strips showing evidence of atrial oversensing, undersensing, or loss of capture

Statistical Analysis Plan

- Programmed parameters (which are necessary to assess if the pauses or minimum heart rate seen on Holter are appropriate or not)
- AV Synchrony
- Appropriate Automatic Mode Switching (AMS) due to atrial arrhythmias
- Reported adverse events and/or subject symptoms with diary entry that is timed and dated to correlate Holter findings with events and/or symptoms.

4.0 DOCUMENTATION AND OTHER CONSIDERATIONS

All analyses will be performed using SAS® for Windows, version 9.2 or higher.

5.0 ACRONYMS AND ABBREVIATIONS

Acronym or Abbreviation	Complete Phrase or Definition
CEC	Clinical Events Committee
IRB	Independent or institutional review board
EC	Ethics Committee
CIP	Clinical Investigation Plan
CRF	Case Report Form
AE	Adverse Event (Non-Serious Adverse Event)
SAE	Serious Adverse Event
ADE	Adverse Device Effect (Non-Serious Adverse Device Effect)
SADE	Serious Adverse Device Effect
UADE	Unanticipated Adverse Device Effect
USADE	Unanticipated Serious Adverse Device Effect
ACE	angiotensin-converting enzyme
ARB	angiotensin II receptor blocker
CFR	Complication-free rate
6MWT	Six-minute walk test
CAEP	Chronotropic Assessment Exercise Protocol
MET	Metabolic Equivalent of Task
LCB	Lower Confidence Bound
AV	Atrioventricular
SAS	Statistical Analysis System
SAP	Statistical Analysis Plan

Statistical Analysis Plan

